9.3.6 Immunizations

Influenza Vaccine

Subjects will be asked to obtain influenza virus vaccine from a primary care provider or community flu vaccine program annually in the fall or winter in accord with current CDC recommendations for patients with diabetes or immunocompromising conditions caused by medications, and also in accord with the American Diabetes Association Standards of Medical Care in Diabetes - 2008.

Pneumococcal Vaccine

Subjects will be asked to obtain at least one pneumococcal vaccine in accord with current CDC recommendations for patients with diabetes or immunocompromising conditions, and also in accord with the American Diabetes Association Standards of Medical Care in Diabetes - 2008. CDC recommends a one-time revaccination if the vaccine was administered > 5 years ago.

Hepatitis Vaccine

Subjects will be asked to obtain a series of hepatitis B vaccine in advance of transplant in accord with current Centers for Disease Control (CDC) recommendations for patients with diabetes or immunocompromising conditions.

10 Additional Information

10.2 Appendices

10.2.1 Appendix "Letter of confirmation by collaborating organ procurement agencies"

10.2.2 Appendix "Pre-Screening"

10.2.3 Appendix "Detailed Visit Schedule"

10.2.4 Appendix "Transplant Order" and "Post-Transplant Orders"

10.2.5 Appendix “HYPO Score sheets”

10.2.6 Appendix “Letter of consent”

10.2.7 Appendix "Certificate of Analysis"

10.2.8 Appendix “Ricordi Chamber”

10.2.9 Appendix..“Transplant Release Form”

10.2.10 Appendix.. "Package Insert Sirolimus"

10.2.11 Appendix ..“Package Insert Prograf®”

10.2.12 Appendix “Package Insert Simulect®”

10.2.13 Appendix "Package Insert Valcyte®"

10.2.14 Appendix "Package Insert Septra®"

10.2.15 Appendix “Package Insert Kefzol®”

10.2.16 Appendix "Package Insert Lovenox®"

10.2.17 Appendix "Package Insert Etanercept"

10.2.18 Appendix “Package Insert Mycophenolate Mofetil”

10.2.19 ***Appendix "Package Insert Thymoglobulin"***

10.2.20 ***Appendix "Package Insert Byetta®"***

10.2.21 *Appendix “Product Monograph Imuran®”*

10.2.22 *Appendix "Collaborative Islet Transplant Registry"*

10.2.23 Appendix "A Novel Beta Cell Specific Microfluidic Perfusion and Imaging Device for Islet Potency Testing Substudy"

Selected Scientific Papers

## ABBREVIATIONS

AE	Adverse event
AIR	Acute insulin response
BUN	Blood urea nitrogen
CGL	Complete graft loss
CIC	Chicago Islet Consortium
CRF	Case report form
CSR	Clinical study report
CVD	Cardiovascular disease
DBP	Diastolic blood pressure
ECG	Electrocardiogram
HepB	Hepatitis B
HepC	Hepatitis C
HIV	Human Immunodeficiency Virus
HYPO	Hypoglycemic
ICH	International Conference on Harmonisation of Technical Requirements for Registration of Pharmaceuticals for Human Use
ITT	Intent-to-treat
IVGTT	Intravenous glucose tolerance test
LLN	Lower limit of normal
MedDRA	Medical Dictionary for Regulatory Activities
OGTT	Oral glucose tolerance test
PCS	Potentially clinically significant
PRA	Panel reactive antibody
PT	MedDRA preferred term
QA	Quality assurance
RBC	Red blood cells
SAE	Serious adverse event
SAP	Statistical analysis plan
SBP	Systolic blood pressure
SHE	Severe hypoglycemic events
SOC	MedDRA system organ class
T1D	Type I diabetes
TEAE	Treatment-emergent adverse event
TCAE	Terminology Criteria for Adverse Events in Trials of Adult Pancreatic Islet Transplantation
ULN	Upper limit of normal
WBC	White blood cell count
WHO	World Health Organization

## **1. INTRODUCTION**

This statistical analysis plan (SAP) is being developed after review of Islet Transplantation at the University of Illinois at Chicago protocol version 0031 (August 7, 2014) and the corresponding case report form (CRF), but before any analyses of the data. The SAP contains detailed information to aid in the performance of the statistical analysis and reporting of the study data for use in the final Clinical Study Report (CSR). This SAP is being written with due consideration of the recommendations outlined in the most recent International Conference on Harmonization (ICH) E9 Guideline entitled Guidance for Industry: Statistical Principles for Clinical Trials and the most recent ICH E3 Guideline entitled Guidance for Industry: Structure and Content of Clinical Study Reports.

This SAP describes the populations that will be analyzed and the patient characteristics, safety, and efficacy parameters that will be evaluated. This SAP provides details of the specific statistical methods that will be used. If additional analyses are required to supplement the planned analyses described in this SAP, they may be completed as *post-hoc* and will be described in detail in the CSR.

## **2. PROTOCOL SUMMARY**

### **2.1. Objectives**

The primary objective of this study is to demonstrate the safety and efficacy of allogeneic islet transplantation in Type 1 diabetic patients performed at the University of Illinois, Hospital and Health Sciences System (UI Health; AKA University of Illinois at Chicago [UIC])

The purpose is to demonstrate that islet transplantation achieves better glycemic control than state-of-the-art insulin treatment in the management of Type 1 diabetic patients with brittle control and a history of severe hypoglycemic episodes with hypoglycemia unawareness. The series of transplants performed with the protocol described herein will provide the basis for a biological license application (BLA) in islet transplantation.

### **2.2. Design and Methodology**

The herein presented protocol is a Phase 3 study. It is a single-center, single-arm, open label trial in which 1-3 allogeneic pancreatic islet transplants per patient will be applied to a total of at least 50 study participants at the University of Illinois at Chicago.

This protocol is designed as a limited series of islet transplants for at least 50 Type 1 diabetic adult patients considered to have brittle diabetes for which glycemic control using insulin is problematic if not impossible.

### **2.3. Planned Number of Patients**

The study plans to perform islet transplants for 50 or more patients. Please see Section 2.8 for sample size and power considerations.

### **2.4. Main Criteria for Inclusion**

Enrolling patients must have Type 1 diabetes mellitus for more than 5 years, complicated by the following situations that persist despite intensive insulin management efforts:

- a. At least one episode of severe hypoglycemia in the past 3 years defined as an event with symptoms compatible with hypoglycemia in which the patient required the assistance of another person, and which was associated with either a blood glucose level < 50 mg/dL (2.8 mmol/L) or prompt recovery after oral carbohydrate, intravenous glucose, or glucagon administration.
- b. Reduced awareness of hypoglycemia, as defined by the absence of adequate autonomic symptoms at capillary glucose levels of < 54 mg/dL (3 mmol/L as reported by the patient).

Please see IND BB-11807 Section 6.4.2 for recipient exclusion criteria.

### **2.5. Treatment Regimens**

#### ***2.5.1 Islet Dosing and Administration***

Allogeneic human islets of Langerhans are a cellular therapy product with systemic effect derived from the pancreas of a cadaveric donor. Islets will be isolated from human pancreases procured from deceased multi-organ donors. A minimum amount of islets of about 10,000 IE/kg recipient body weight is required for engraftment and confirmed C-peptide expression based on the Edmonton series.

This form of procedure may require multiple transplants in order to reach this desired minimum number of islets, as previous clinical studies were unable to reliably reach insulin independence with a single transplant. Eligibility criteria for subsequent islet transplant(s) are described in Section 6.5.1 of IND BB-11807.

The islets of Langerhans mixture will be delivered either: 1) slowly into the portal vein via a syringe attached to a catheter hub or using an infusion bag or 2) by transvenous access to the right jugular vein via an ultrasound guided Microstik. A guiding sheath is advanced through the right atrium and into the right hepatic vein. Position is confirmed with injection of contrast medium.

Further details of the islet transplant procedure can be found in Section 6.5.1 of IND BB-11807.

### ***2.5.2 Immunosuppression Regimens***

Participants in the trial will receive immunosuppression using agents approved by the FDA for organ transplantation and evaluated for use in human islet transplantation under IND to prevent allotransplant rejection. Beginning with the initial transplant, a steroid free immunosuppressive regimen will be administered to all patients. Patients will receive initial doses of basiliximab, sirolimus, low dose tacrolimus, and etanercept. Patients presenting with preformed antibodies against human leukocyte antigens will receive a more intense induction protocol with the addition of a polyclonal anti-T-cell antibody preparation (Thymoglobulin) instead of basiliximab for the initial transplant. Sirolimus and tacrolimus will be given according to the Edmonton protocol. In addition, participants will receive etanercept. Mycophenolate mofetil may be used for patients who do not tolerate the adverse effects of sirolimus or tacrolimus. Other immunosuppressant medications may be used for patients who do not tolerate the adverse effects of sirolimus, tacrolimus, or mycophenolate mofetil. If azathioprine is planned, the patient may be tested for the presence of thiopurine methyltransferase (TPMT).

Please see Section 6.5.2 of IND BB-11807 for the detailed schedule of immunosuppression medications.

### ***2.5.3. Other Medications***

Exenatide will be administered at a dose of 5 mcg subcutaneously given with 1 hour pre-transplant and post-transplant bid for 1 week at any time within a 60 minute period before or after the morning and evening meals. After 1 week of therapy, if tolerated well, the dose will be increased to 10 mcg bid. Exenatide will be given for a total of 6 months after the last islet transplant and may be extended if necessary

In addition to prolonged immunosuppression, transplant patients routinely need other medications. These include the use of prophylactic anti-infective drugs used in patients receiving prolonged immunosuppression. Anti-infective drugs used under this protocol include trimethoprim / sulfamethoxazole for a minimum period of six months, and valganciclovir (Valcyte®) for 3 months post-transplant. With the use of prophylactic anti-infective drugs, total WBC counts and kidney function will be monitored at routine visits. If total WBC counts fall below 3,000, or if other conditions warrant a change in prophylaxis, sulfamethoxazole will be discontinued and substituted with pentamidine 300 mg by inhalation each month for a minimum of six months.

During the transplant procedures, additional medications, local anesthetics, and contrast media are also used. Heparin is used during the transplant to reduce coagulation risks that may lead to liver thrombosis. And for 1 week following the transplant, subcutaneous longer acting, low molecular weight heparin (enoxaparin, Lovenox®) is used. Study patients will be monitored for hemorrhage and bruising while receiving these anticoagulants.

Other medications may be required according to medical conditions presenting during the study period, and will be given according to best medical practice.

## **2.6. Duration of Treatment**

The study duration will be approximately 10 years. The study will consist of a Screening/Baseline Phase, a Treatment Phase, and a Follow-up Phase. The Screening/Baseline Phase will consist of clinical and laboratory evaluations done at the first screening and repeated every 3 months (or 6 months for some, if needed) during the period awaiting the first transplant. The Treatment Phase will consist of Immediate Pre-Transplant Work-up, Transplant Period and Early Post-Transplant Period, all of which span from the moment a patient is admitted to the transplant unit up to when he/she is discharged after transplant, per protocol. Patients will remain in-clinic for a minimum of 24 hours post-transplant until the protocol-defined discharge criteria are met during the Treatment Phase. The Follow-up Phase includes continuous in-home monitoring of glucose levels and scheduled clinic visits that occur on an outpatient basis and will consist of efficacy and safety assessments for a period of 52 weeks post-transplant, followed by additional follow-up for up to 10 years (see Section 17.1 Schedule of Assessments for details). Individual patients will receive one or more transplants as needed as pre-determined by protocol and will be evaluated for efficacy and monitored for safety for up to 10 years following the last transplant.

## **2.7. Criteria for Evaluation**

### **2.7.1 Safety:**

Safety assessments will be performed during the Screening/Baseline Phase, prior to and following the islet cell transplant during the Treatment Phase (at specified times), and during the Follow-up Phase.

Safety of islet cell transplantation in Type 1 diabetes depends primarily on determining the incidence of serious and unexpected complications or adverse events. The surgical implantation procedure has associated risk and complications of the islet cell infusion will be followed closely. The post-transplant immunosuppression regimen also has expected toxicities, both acute and chronic. Laboratory measures and signs and symptoms will be followed at specified intervals. Some of these measures are often more subjective and

variable in nature, but should provide a clear indication of relative safety for patients enrolled in this study.

All study participants who receive an islet cell transplant will be followed for safety up to 1 year following the last transplantation or up to the data cut-off date, 13 April 2015. The safety of the islet transplantation and associated immunosuppressive therapies will be evaluated by analysis of adverse experiences, clinical laboratory tests, and physical examination. Safety events will be analyzed by their incidence, severity, and relationship to islet cell transplantation. In particular, the following parameters are of primary interest in assessing the clinical safety of islet cell transplantation:

One year after first and the last islet transplants we will evaluate:

a. Procedure Related Events

The incidence and severity of adverse events related to the islet infusion procedure including:

- Bleeding (> 2 g/dl decrease in hemoglobin concentration)
- Portal vein thrombosis, branch or main
- Biliary puncture
- Wound complication (infection or subsequent hernia)
- Increased transaminase levels (> 5 times upper level of normal)

b. Immunosuppression Related Events

The incidence and severity of adverse events related to immunosuppression including allergy:

- Reduction in GFR (> 25% reduction in estimated GFR from baseline by Cockcroft and Gault formula)
- Increase in urinary albumin excretion
  - New onset microalbuminuria (albumin > 30 mg/day confirmed by 24 hour urine collection) in patients who were previously within normal limits
  - For those patients with baseline microalbuminuria (30-300 mg/day), new onset overt albuminuria (greater than 300 mg/day confirmed by 24 hour urine collection)
- Panel Reactive Antibody (PRA, please see Section 2.9 Changes from the Planned Protocol Analysis)
- Addition or intensification of antihypertensive therapy
- Oral ulcers
- Lower extremity edema
- Gastrointestinal toxicity (diarrhea)
- Neutropenia (neutrophils < 1.3 thous/ $\mu$ L)
- Anemia (hemoglobin men < 12.1, women < 11.7 g/dL)
- Thrombocytopenia (platelets < 150 thous/ $\mu$ L)
- Infections (viral, bacterial, or fungal)

- Neoplasms, benign or malignant

Severity will be graded according to Collaborative Islet Transplant Consortium *Terminology Criteria for Adverse Events (TCAE) In Trials of Adult Pancreatic Islet Transplantation, Version 5.0 (03 August 2011)*

### **2.7.2 Efficacy:**

#### **a. Primary Efficacy Endpoint:**

The proportion of patients with an HbA1c  $\leq 6.5\%$  and free of severe hypoglycemic events at 1 year after the first and 1 year after the last islet cell infusion, respectively (for the addition of time point see Section 2.9 Changes from the Planned Protocol Analysis).

Standard insulin treatment can rarely improve glycemic control in brittle Type 1 diabetic patients who are already on state-of-the-art insulin therapy. The rate of aforementioned favorable outcome achieved under standard insulin treatment over-a-year from a population-based diabetes registry database is as low as 0.3% (Tiwari et al., 2012). In general these patients require insulin reduction to reduce hypoglycemic episodes, which would likely lead to higher HbA1c. In contrast, islet transplantation can reduce hypoglycemic episodes without increasing HbA1c.

The protocol definition of severe hypoglycemic event: An event with symptoms compatible with hypoglycemia in which the patient required the assistance of another person and which was associated with either a blood glucose level  $< 50$  mg/dl (2.8 mmol/L) or prompt recovery after oral carbohydrate, intravenous glucose, or glucagon administration.

A broader clinical definition of severe hypoglycemic event that will apply to some of the exploratory endpoints as described later: receiving any of third-party assistance to treat a hypoglycemic reaction would sufficiently determine the occurrence of a SHE, regardless of blood glucose levels which may or may not be available.

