6.5 Test Material and Administration

6.5.1 Islet Dosing and Administration

A minimum amount of islets of about 10,000 IE/kg recipient body weight is required for engraftment and confirmed C-peptide expression based on the Edmonton series. This form of procedure may require multiple transplants in order to reach this desired minimum number of islets, as previous clinical studies were unable to reliably reach insulin independence with a single transplant.

Eligibility for second or third islet infusion

Subjects are eligible for further transplant if by the end of the fourth week after the first islet infusion or by the end of the fourth week after the second islet infusion they do not meet insulin-independence criteria. If a subject does not reach the definition of insulin independence by the end of the third month after the third transplant, the subject may be considered for an exceptional fourth islet infusion. However, the indication for an exceptional fourth transplant needs to be presented to the Data Monitoring Committee and approval obtained.

Eligibility for islet retransplantation and/or fourth islet transplant:

Subjects are eligible for subsequent islet infusions if after a period of insulin independence of at least 30 days, they present with declining islet function requiring reintroduction of exogenous insulin. Subjects may receive this additional islet infusion anytime during the first year after the last islet infusion, or anytime during the 5-year follow-up, as long as no exclusion criteria are present and avoiding any HLAs (human leukocyte antigens) against which the recipient may have developed donor specific antibodies.

No maximum number of delivered islets is specified, except that the number must exceed 10,000 IE/kg following 2 islet transplants, and packed cell volume may not exceed 10 mL per transplant.

Transplant Procedure

Islets will be isolated from human pancreases procured from deceased multi-organ donors as described in Section 7. The islet isolation procedure will be performed in the clean room facilities of the Cell Isolation Laboratory at the University of Illinois at Chicago Hospital (see Section 7.4 *University of Illinois at Chicago Islet Processing Facility*). Isolated human pancreatic islets will be stored for a maximum of 12 hours before transplantation (see Section 7.2 *Product Manufacturing*).

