6.10.2 Efficacy

Specification of Efficacy Parameters

a. Primary Efficacy Endpoint:

The proportion of subjects with an HbA1c \leq 6.5% and free of severe hypoglycemic events at 1 year after the first islet cell infusion

Standard insulin treatment can rarely improve glycemic control in brittle Type 1 diabetic patients who are already on state-of-the-art insulin therapy. In general these patients require insulin reduction to reduce hypoglycemic episodes, which would likely lead to higher HbA1c. In contrast, islet transplantation can reduce hypoglycemic episodes without increasing HbA1c.

Definition of severe hypoglycemic event: An event with symptoms compatible with hypoglycemia in which the subject required the assistance of another person and which was associated with either a blood glucose level < 50 mg/dl (2.8 mmol/L) or prompt recovery after oral carbohydrate, intravenous glucose, or glucagon administration.

For the primary endpoint (composite HbA1c \leq 6.5% and absence of severe hypoglycemic events), we expect 80% of the transplant population to achieve this endpoint. Therefore, assuming a sample size of 50, a two-sided 95.0% confidence interval for a single proportion will extend \pm 0.111 from the observed proportion. When the sample size is 40, a two-sided 95.0% confidence interval for a single proportion will extend \pm 0.124 from the observed proportion. Proportion and surrounding confidence interval will be reported.

Figure 2. Sample Size Curve for 95% Confidence Interval for Proportion

[figure not shown]
[figure not shown]

Figure 3 illustrates the cumulative percent of patients achieving HbA1c reduction from baseline in Phase1/2. As shown, all patients experienced a reduction in HbA1c (decrease of 0.6 to 2.7%). Furthermore, all patients presented with a HbA1c \leq 6.5 one year after final transplant.

Figure 3. Cumulative Percent of Patients Attaining HbA1c Reduction from Baseline at 1 Year after Last Transplant (N=7).

b. Secondary Efficacy Endpoints:

The secondary efficacy endpoints will focus on more detailed analysis of glycemic control, and will include the following:

1. **Insulin independence:** We will evaluate the proportion of subjects presenting with insulin independence while fulfilling the primary endpoint.

Definition of insulin-independence:

- Absence of exogenous insulin injection
- HbA1c \leq 6.5%

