## **2.9. Changes from the Planned Protocol Analysis**

A second definition of SHE was added in addition to the protocol definition for exploratory analysis. The protocol definition tends to exclude some clinically valid SHEs with a more limiting blood glucose parameter. The purpose of using the second definition is to compare the SHE outcomes by this broader clinical definition with that by the protocol definition, and to demonstrate that the efficacy evaluation is not biased by the differential definitions of SHE.

Evaluation of PRA was omitted in the protocol and is added back as a critical safety endpoint based on its clinical significance.

The original protocol-planned evaluation of primary and secondary endpoints was scheduled at 1 year following the first transplant. The evaluation and analyses are also planned for the time point at 1 year after last transplant in order to take into consideration that patients can have more than one transplant, and thus the 1-year-post-last-transplant evaluation is important in providing adequate efficacy assessment.

For the secondary endpoint based on patient self-monitored post-prandial capillary glucose levels, the evaluation minimum requirement is reduced from three out of 21 times a week to a proportionally one out of every seven times measured. The change is based on the consideration that this piece of information relies totally on patient reported diary data, and frequent and random missing of data is expected. The reduction of minimum data requirement here is an attempt to unbiased efforts in maximizing the reportable results.

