## **9. EFFICACY EVALUATIONS**

### **9.1. Analysis of Primary Endpoints**

The primary endpoint is the proportion of patients with 1) an HbA1c  $\leq$  6.5% at Day 365, AND 2) free of severe hypoglycemic events (for definition see Section 2.7.2a) from Day 28 to Day 365, inclusive, following the first and the last islet transplant, respectively, with the day of corresponding transplant designated Day 0.

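### The SAP adds a second primary time point, 1 year after the last infusion, without saying which result decides, and that clock restarts at re-infusion

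*SAP*

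**What the plan says.** **Protocol 6.10.2** defines the primary endpoint as the proportion of subjects with HbA1c at or below 6.5% and "free of severe hypoglycemic events at 1 year after the first islet cell infusion". No other time point is named for it.

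**SAP 2.7.2a** assesses the same composite "at 1 year after the first and 1 year after the last islet cell infusion, respectively". SAP 9.1 repeats this, "following the first and the last islet transplant, respectively, with the day of corresponding transplant designated Day 0", and counts SHEs "from Day 28 to Day 365, inclusive" on each clock. SAP 9.1.1 applies both clocks to all treated patients. Table 14.2.1 prints the two results as parallel columns, each with its own 95% confidence interval.

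**SAP 2.9** discloses the change: "The original protocol-planned evaluation of primary and secondary endpoints was scheduled at 1 year following the first transplant". Its reason is that patients may have several transplants, so that "the 1-year-post-last-transplant evaluation is important in providing adequate efficacy assessment". It does not rank the new time point against the old one.

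**Protocol 6.5.1** makes a subject eligible for a further infusion if insulin independence is not met four weeks after the first or second infusion. A subject whose graft declines after at least 30 days of insulin independence is also eligible: "Subjects may receive this additional islet infusion anytime during the first year after the last islet infusion, or anytime during the 5-year follow-up". The SAP sets no limit on when the last infusion may fall.

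**The concern.** Two results carry the label primary. The SAP gives no order, no alpha split, no requirement that both succeed and no success criterion, so either column could become the headline. That matters because the trial has no control arm and is meant to support a license application; the primary proportion is the main efficacy evidence.

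The two columns also differ in kind. The first clock starts at a fixed point for everyone. The last clock starts at a date that depends on how the patient has done. For a re-infused patient the last-infusion column drops HbA1c at 1 year after the first infusion, and every SHE up to Day 27 after the last infusion. A patient infused once has the same result in both columns. The Phase 1/2 HbA1c results shown beside the 80% expectation in protocol 6.10.2 (N=7) are also taken at 1 year after the last transplant.

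**Working it through.** **1. The plan's own figures.** The half-widths in SAP 2.8 reproduce: 1.96 × √(0.8 × 0.2 / 50) = 0.111, and 0.124 with n=40. SAP Table 1 reproduces with a normal approximation, one-sided 0.05 and a bar of 0.3% + 50 points = 50.3%:

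Φ[(p − 0.503) / √(p(1−p)/n + 0.003 × 0.997/n) − 1.645]

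At n=15 and p=0.80 this gives 88.6% (stated 88%). At n=50 and p=0.70 it gives 91.5% (stated 91.5%). These figures are for one endpoint at the full 0.05.

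**2. Two looks, with re-infusion not changing the success rate.** Assume a true 50% on both clocks. Single-infusion patients have one result for both; multiply infused patients have an independent second draw. An exact one-sided 5% test against 50% needs 32/50 or 12/15. By simulation (400,000 runs per setting), with 25% to 100% of patients infused more than once, the chance that at least one column passes is:

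- n=50: 5.2% to 6.4%, against 3.2% for one column
- n=15: 2.8% to 3.5%, against 1.8% for one column

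For scale, 6 of the 10 Phase 1/2 subjects in protocol 4.1.3 had two or three infusions.

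**3. Outcome-dependent restart.** Let p be the first-clock success rate, f the share of first-clock failures re-infused, g the share of first-clock successes re-infused, and s the last-clock success rate of re-infused patients. Then:

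last-clock rate = p + (1−p) f s − p g (1−s)

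The documents give none of f, g or s, so the table is a range of assumptions starting from p=50%. Pass probabilities are exact binomial, at 32/50 and 12/15.

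| f | g | s | Last-clock rate | Pass, n=50 | Pass, n=15 |
|---|---|---|---|---|---|
| 0.5 | 0.5 | 0.5 | 50% | 3.2% | 1.8% |
| 0.2 | 0 | 0.3 | 53% | 7.8% | 3.0% |
| 0.5 | 0.25 | 0.5 | 56.3% | 16.8% | 5.2% |
| 0.4 | 0 | 0.5 | 60% | 33.6% | 9.1% |
| 0.5 | 0 | 0.5 | 62.5% | 47.6% | 12.7% |
| 0.6 | 0 | 0.5 | 65% | 62.2% | 17.3% |
| 0.6 | 0 | 0.7 | 71% | 89.2% | 32.7% |

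On the first clock the pass probability is 3.2% at n=50 and 1.8% at n=15 throughout. Example for the third row: 0.5 + 0.5 × 0.5 × 0.5 − 0.5 × 0.25 × 0.5 = 0.5625.

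**4. The planned interval.** SAP 9.1.1 plans a two-sided 95% Clopper-Pearson interval. Its lower limit exceeds 50% from 33/50 (51.2%; 32/50 gives 49.2%) and from 12/15 (51.9%). With the n=50 cut-off at 33, the 62.5% row passes 36.2% of the time and the first clock 1.6%. At n=15, two failures converted to successes turn 10/15 into 12/15.

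**5. Cost of alternatives.** With the first infusion as sole primary, SAP Table 1 stands as it is. Splitting alpha equally (1.96 in place of 1.645) cuts power at n=15 and p=0.80 from 88.6% to 81.3%.

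**The case against.** The addition is declared in SAP 2.9, and SAP 1 places the plan before any analysis. Treatment is a course of one to three infusions, so outcome after the completed course is a fair question. The protocol already uses both clocks for safety (6.10.1) and continuous glucose monitoring (6.10.2). All of this stands. It supports reporting the last-infusion result, but it does not say which result leads.

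Three stronger readings are tempting, and the documents do not support them.

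- *A reader might infer that first-year failures are overwritten.* They are not. Table 14.2.1 keeps the first-infusion column on the same ITT population, Listing 16.2.6a gives patient-level results at 1 year after the first transplant, and Table 14.1.8 lists every infusion. Failures drop out only within the added column.
- *A reader might infer that failures get a new start and successes never do.* The trigger is insulin independence, not the composite. A patient with HbA1c at or below 6.5%, no SHE and continuing insulin is a primary success and still eligible for re-infusion; so is a success who later declines. Either can then fail on the last clock. The first clock also already credits re-infusions within the first year (SAP 9.1.1). And a patient re-infused less than a year before the 13 April 2015 cut-off could be imputed a last-clock failure under SAP 9.1.2.
- *A reader might take a figure such as 47.6% as a false-positive rate.* In that scenario the true last-clock rate is 62.5%, so passing a 50% bar is a correct finding about a different quantity. The planned analysis is also an interval with no pass/fail rule; the one-sided 0.05 level appears only in the power section.

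**Conclusion.** The gap is real: the protocol has one primary time point, the SAP has two, and no text says which decides. The last-infusion column starts from an outcome-dependent date and forgives earlier failures within that column.

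The bias is probably upward, because re-infusion goes to patients lacking or losing insulin independence. Its sign and size rest on who is re-infused and how they fare, which the documents do not give. Over the assumed range, a 50% first-clock rate goes with a last-clock rate of 50% to 71%, and the chance of clearing a 50% bar by the one-sided exact test runs from 3% to 89% at n=50 and from 2% to 33% at n=15. These illustrate how far the two columns can diverge; they are not error rates. Having two looks matters little by itself: about 5% to 6% at n=50 if re-infusion leaves the success rate unchanged. What needs settling is which quantity is the headline.

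**What to change.** In SAP 2.7.2a, SAP 9.1 and Table 14.2.1, name 1 year after the first infusion as the sole primary endpoint, as in protocol 6.10.2. Label 1 year after the last infusion as supportive. Add a row to Table 14.2.1 cross-classifying the two results, with counts of patients going from failure to success and from success to failure, so that a reader can see how much of any difference comes from the restart.

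The cost is SAP wording and one table row. No data are lost, and alpha and SAP Table 1 are unchanged. The downside for the sponsor is that the headline rate may be less favourable.
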